## CLINICAL PROTOCOL SUMMARY SHEET

**STUDY TITLE:** A Pilot Evaluation of BLI4700 Bowel Preparation Administered as a One Day, Split-Dose Regimen in Adult Subjects

**PROTOCOL:** BLI4700-202

**VERSION DATE:** 16 February 2017

**IND NUMBER:** 124,988

**STUDY PHASE:** 2

**OBJECTIVE:** To evaluate the safety and efficacy of BLI4700 tablets administered as a one day, split-dose regimen prior to colonoscopy in adult patients.

**STUDY DESIGN:** This will be an open-label, multi-center study.

**SUBJECTS:** Up to 60 male and female adult subjects will be enrolled.

**STUDY MEDICATIONS:** BLI4700 tablets

**DURATION:** Subject participation in this study may last up to 37 days.

**EFFICACY ENDPOINTS:** Efficacy will be based on overall preparation success as determined by the colonoscopist. Additional efficacy measures include the proportion of excellent preparations, segmental cleansing, time to cecum, volume of intraprocedural water used to improve visualization, percent of procedures that reach the cecum.

**SAFETY ENDPOINTS:** Safety endpoints include:

- Adverse event reports
- Changes in serum chemistry parameters.
- Subject reported prep-related symptoms

## 1. INTRODUCTION

### **Background**

Colorectal cancer (CRC) is a leading cause of cancer death. The lifetime risk of developing CRC in the US approaches 6%, and almost half of those affected will die of the disease. Despite the usefulness of screening procedures for its detection, CRC is a major cause of morbidity and mortality. In screening procedures for CRC such as sigmoidoscopy, colonoscopy, and radiography, it is important that the colon be thoroughly purged and cleansed. In particular, it is essential that as much fecal matter and fluids as possible be removed from the colon to permit adequate visualization of the intestinal mucosa.

### **Preliminary Experience with the Similar Bowel Preparations**

Two Phase 3 studies were conducted comparing BLI800 (SUPREP) to the FDA approved preparation MoviPrep. The BLI800-301 study evaluated BLI800 as a one-day preparation, completed on the day prior to colonoscopy. The BLI800-302 study utilized a two-day (or “split-dose”) regimen in which half the preparation was taken the evening prior to colonoscopy, and the remaining half completed on the morning of the procedure.

The primary efficacy analysis in both Phase 3 studies supported the conclusion that BLI800 is equivalent to MoviPrep with respect to cleansing efficacy (cumulative data shown below in Table 1).

**Table 1**  
Primary Efficacy Responder Analysis  
BLI800-301/302 Studies

Responder 	BLI800 n (%)	MoviPrep n (%)	95% CI	p 	p 
All Patients (n)	375	376			
Success	334 (89.5%)	330 (87.8%)	-2.8, 6.3	0.410	<0.001
Fail	39 (10.5%)	46 (12.2%)			
301 Patients (n)	194	193			
Success	159 (82.4%)	155 (80.3%)	-5.7, 9.8	0.614	<0.001
Fail	34 (17.6%)	38 (19.7%)			
302 Patients (n)	181	183			
Success	175 (97.2%)	175 (95.6%)	-2.2, 5.4	0.391	<0.001
Fail	5 (2.8%)	8 (4.4%)			

(1) A successful treatment is defined as bowel cleansing graded either excellent or good by the blinded colonoscopist (grading score = 3 or 4).

(2) P-value for the difference between treatments

(3) P-value for the non-inferiority hypothesis using an equivalence margin of 15 percent

The breakdown of cleansing efficacy by study and by preparation grade is shown below in Table 2. The data indicate that a two day preparation regimen, as performed in the 302 study, produces markedly superior cleansing results over a one day preparation, as in the 301 study. In each study and overall, BLI800 achieved a greater number of excellent preparations than MoviPrep. This difference resulted in a higher Mean Preparation Score for BLI800, reaching statistical significance (p = 0.049) in the total population.

**Table 2**  
Preparation Cleansing Score  
BLI800-301/302 Studies

Score	All Patients		301 Patients		302 Patients	
	SUPREP n (%)	MoviPrep n (%)	SUPREP n (%)	MoviPrep n (%)	SUPREP n (%)	MoviPrep n (%)
4 Excellent	200 (53.6%)	168 (44.7%)	86 (44.6%)	72 (37.3%)	114 (63.3%)	96 (52.5%)
3 Good	134 (35.9%)	162 (43.1%)	73 (37.8%)	83 (43.0%)	61 (33.9%)	79 (43.2%)
2 Fair	25 (6.7%)	37 (9.8%)	22 (11.4%)	31 (16.1%)	3 (1.7%)	6 (3.3%)
1 Poor	11 (2.9%)	8 (2.1%)	9 (4.7%)	6 (3.1%)	2 (1.1%)	2 (1.1%)
Mean Score	3.41	3.31	3.24	3.15	3.59	3.47
p value	0.049		0.278		0.050	

Adverse events were also evaluated in the Phase III studies. The only treatment emergent adverse event category with a frequency greater than 3% was gastrointestinal (BLI800 = 4.5% and MoviPrep = 4.3%). The expected symptoms of nausea and vomiting were the most frequent (1.3% each) within the gastrointestinal category. There was no difference between BLI800 and MoviPrep in the frequency of any treatment-emergent adverse events, including those that were gastrointestinal in origin. No clinically significant differences between groups were seen in laboratory testing of serum chemistry and hematology. At the one month follow-up visit, no change in serum creatinine was observed for BLI800 patients.

A smaller Phase III study (n = 136) was conducted comparing the safety and efficacy of SUPREP (in the FDA approved split-dose regimen) to NuLYTELY. In addition to preparation success (as defined above), the blinded colonoscopist also rated the amount of residual fluid and stool in each colon segment. As shown below in Tables 3 and 4, SUPREP was superior to NuLYTELY in overall preparation success, as well as in reducing the amount of residual stool and fluid in most colon segments (most importantly the right colon, a segment with higher miss rates for polyps and flat lesions).

**Table 3**  
Primary Efficacy Responder Analysis  
Number and Percent of Successful Preparations

Responder	SUPREP n	NuLYTELY n	95% CI	P
All Patients (n)	63	67		
Success	62 (98.4%)	60 (89.6%)	0.9, 16.8	
Fail	1 (1.6%)	7 (10.4%)		0.038

(1) A successful treatment is defined as bowel cleansing graded either excellent or good by the blinded colonoscopist (grading score = 3 or 4).

(2) P-value for the difference between treatments

**Table 4**  
Investigator Grading of Preparations by Segment

Symptom (score)	Residual Stool		Residual Fluid	
	SUPREP (n=63)	NuLYTELY (n=67)	SUPREP (n=63)	NuLYTELY (n=67)
Cecum				
Absent	57 (91%)	45 (67%)	27 (43%)	10 (15%)
Small	6 (9%)	15 (22%)	28 (44%)	42 (63%)
Moderate	0	3 (5%)	8 (13%)	10 (15%)
Excess	0	0	0	1 (2%)
P 	0.010		0.004	
Ascending (Right) Colon				
Absent	57 (91%)	46 (69%)	40 (64%)	24 (36%)
Small	6 (9%)	16 (24%)	23 (36%)	29 (43%)
Moderate	0	1 (2%)	0	10 (15%)
Excess	0	0	0	0
P 	0.020		< 0.001	
Transverse Colon				
Absent	58 (92%)	55 (82%)	43 (68%)	33 (49%)
Small	5 (8%)	6 (9%)	20 (32%)	20 (30%)
Moderate	0	1 (2%)	0	9 (13%)
Excess	0	1 (2%)	0	1 (2%)
P 	0.644		0.005	
Descending Colon				
Absent	58 (92%)	56 (84%)	42 (67%)	26 (39%)
Small	5 (8%)	6 (9%)	17 (27%)	32 (48%)
Moderate	0	1 (2%)	4 (6%)	5 (8%)
Excess	0	0	0	0
P 	0.763		0.013	
Sigmoid Colon/Rectum				
Absent	59 (94%)	54 (81%)	40 (64%)	32 (48%)
Small	3 (5%)	7 (10%)	20 (32%)	28 (42%)
Moderate	1 (1%)	3 (5%)	3 (5%)	5 (8%)
Excess	0	2 (3%)	0	0
P 	0.173		0.283	
 P-value for difference between treatments				

There were no deaths or serious adverse events for patients who received SUPREP in this study. No statistically significant differences between the preparations with respect to adverse events were detected in the elderly population or overall. The number of events expected with gastrointestinal cleansing agents (e.g. nausea, bloating and cramping) was insignificant. Differences in laboratory results were considered by investigators to be clinically insignificant.

The BLI800-301 and BLI800-302 studies supported the FDA's determination that SUPREP was safe and effective in adults undergoing colonoscopy, leading to its FDA approval in August 2010.

As a condition of the SUPREP approval, FDA required Braintree Laboratories to conduct several post marketing studies in order to further demonstrate the safety of SUPREP in special populations (the elderly, and those with renal or hepatic impairment) and to look for rare occurring serious adverse events. In study BLI800-440 (PMR 1580-7), patients in special populations (renal/hepatic/elderly) took SUPREP prior to colonoscopy and were followed for 6 months. 184 patients took SUPREP in this study, which also included non-special population patients (e.g. patients undergoing screening colonoscopy). SUPREP was shown to be safe in all of these patient groups in near term and long term follow up, comparable to the GoLYTELY comparator used in the study.

Studies BLI800-430 and BLI800-431 (PMR 1580-8) evaluated the safety of SUPREP in special populations (renal/hepatic/elderly) through repeated ECG measurements. A total of 37 patients completed the study and no significant ECG changes were seen after patients took two SUPREP doses 2 hours apart (acute administration).

For study BLI800-450 (PMR 1580-6), a large retrospective review of electronic medical records and insurance claims was conducted to tabulate the rates of specific serious adverse events (e.g. cardiac events, renal failure, ischemic colitis) occurring within 3 months of patients taking SUPREP. Claims data on approximately 33,000

SUPREP patients and 266,000 control patients was analyzed, revealing no difference between groups for serious adverse events of interest.

**Preliminary Development of BLI4700**

The goal of the current study is to evaluate the safety and efficacy of BLI4700 given in a one day, split-dose regimen prior to colonoscopy in adult patients.

## **2. STUDY OBJECTIVE**

The objective of this study is to evaluate the safety and efficacy of BLI4700 as a bowel preparation prior to colonoscopy in adult patients.

## **3. STUDY PLAN**

### **3.1. Study Design**

This is an open-label, multi-center study in adult subjects.

### **3.2. Number of Subjects**

Up to 60 male and female subjects who are undergoing colonoscopy for routinely accepted indications will be enrolled in this study.

### **3.3. Duration of Study**

Subject participation in this study will last up to 37 days. A screening visit (Visit 1) should be performed within 30 days of the colonoscopy. Subjects meeting all eligibility criteria will be enrolled to receive BLI4700. Subjects will return to the clinic the day of

colonoscopy (Visit 2). Subjects with clinically significant laboratory abnormalities and/or ongoing adverse events related to the study preparation may return for a follow up visit 7 days after colonoscopy.

### **3.4. Study Preparations**

#### **BLI4700 Tablets**

Multiple BLI4700 formulations consisting of two 12 tablet doses may be evaluated in this trial. The two formulations contain the following active ingredients in solid form:

#### Formulation #1

Material and Grade	BLI4700 #1 (24 tablets)
Sodium Sulfate	
Potassium Bicarbonate	

#### Formulation #2

Material and Grade	BLI4700 #2 (24 tablets)
Sodium Sulfate, USP	
Potassium Bicarbonate	
Magnesium Chloride	

Subjects will consume a total of 24 tablets (two 12 tablet doses). Each tablet dose will be contained in a separate bottle. The bottles will have a clinical label containing a caution statement, study code, study sponsor and kit number. Subjects will be provided with instructions on how to complete the preparation.

Any additional formulations evaluated under this protocol will require a formal amendment and IRB approval prior to enrollment of subjects.

### **3.5. Subject Selection**

#### **3.5.1. Inclusion Criteria**

Subjects will be admitted to the study if they are:

1. Male or female outpatients who are undergoing colonoscopy for a routinely accepted indication, including (but not limited to):
  - Routine screening
  - Polyp or neoplasm history
  - Rectal bleeding
  - Other gastrointestinal bleeding
  - Abdominal pain
  - Unknown diarrhea or constipation etiology
  - Anemia of unknown etiology
  - Inflammatory bowel disease
  - Abnormal endosonography
  - Evaluation of barium enema results
  - Laser therapy
2. At least 18 years of age
3. Subjects must be scheduled for an afternoon colonoscopy (12:00PM or later)
4. If female, and of child-bearing potential, is using an acceptable form of birth control (hormonal birth control, IUD, double-barrier method, depot contraceptive, abstinent, or vasectomized spouse). Subjects practicing abstinence must agree to use an acceptable form of birth control should they become sexually active during the study. Pharmacologic methods of contraception must be stable for at least one month prior to Visit 1 and remain stable through completion of the study.
5. Negative urine pregnancy test at screening, if applicable
6. In the Investigator's judgment, subject is mentally competent to provide informed consent to participate in the study

#### **3.5.2. Exclusion Criteria**

Subjects who meet any of the following criteria will be excluded from the study:

1. Subjects with dysphagia or an aversion to swallowing tablets.
2. Subjects with known or suspected ileus, severe ulcerative colitis, gastrointestinal obstruction, gastric retention, bowel perforation, toxic colitis or megacolon.
3. Subjects who had previous significant gastrointestinal surgeries (e.g. colostomy, colectomy, gastric bypass, stomach stapling). Any questions regarding the

significance of a previous gastrointestinal surgery should be directed to Braintree Laboratories.

4. Subjects with uncontrolled pre-existing electrolyte abnormalities, or those with clinically significant electrolyte abnormalities based on Visit 1 laboratory results, such as hypernatremia, hyponatremia, hyperphosphatemia, hypokalemia, hypocalcemia, dehydration, or those secondary to the use of diuretics or angiotensin converting enzyme (ACE) inhibitors.
5. Subjects with a prior history of renal, liver or cardiac insufficiency (including congestive heart failure or other significant cardiac abnormality) that the investigator feels is clinically significant and should rule out the subject from participation in the study.
6. Subjects with impaired consciousness that predisposes them to pulmonary aspiration.
7. Subjects undergoing colonoscopy for foreign body removal and/or decompression.
8. Subjects who are pregnant or lactating, or intending to become pregnant during the study.
9. Subjects of childbearing potential who refuse a pregnancy test.
10. Subjects allergic to any preparation components.
11. Subjects who, in the opinion of the Investigator, should not be included in the study for any reason, including inability to follow study procedures.
12. Subjects who have participated in an investigational surgical, drug, or device study within the past 30 days.
13. Subjects who withdraw consent before completion of Visit 1 procedures.

#### **4. STUDY PROCEDURES**

Study procedures are described as follows and depicted graphically in Section 4.5, below.

##### **4.1. Visit 1**

Following the informed consent process, the subjects will sign a consent form. Subject's demographics and concomitant medications will be recorded, vital signs will be obtained (including height (visit 1 only), weight, pulse, orthostatic blood pressure), and a physical examination will be performed. Medical history will be recorded to include all ongoing conditions at Visit 1 as well as any significant conditions, defined

as:

Abdominal surgeries, Renal failure/dysfunction, Liver failure/dysfunction, Cardiac disorders (e.g. myocardial infarction, coronary artery disease tachycardia), Hypertension, Diabetes, Cancer (must indicate type of cancer), Electrolyte abnormalities

Blood samples will be collected for testing. Colonoscopies must be scheduled to allow for receipt of laboratory results prior to the day the subject is scheduled to begin preparation.

**Serum Chemistry:** Alkaline Phosphatase, ALT, anion gap (calculated), AST, bicarbonate, total bilirubin, blood urea nitrogen, calcium, chloride, creatinine kinase, creatinine, eGFR (calculate), GGT, magnesium, phosphorus, potassium, sodium, total protein and uric acid

A urine pregnancy test will be performed on female subjects of childbearing potential (see Section 4.7). Subjects meeting all entry criteria will be eligible for enrollment.

#### **4.1.1. Study Drug**

Eligible subjects will be provided with instructions on how to use the study preparation. Subjects will self-administer the study preparation starting the morning of their scheduled colonoscopy according to the instructions provided by the study site (full preparation instructions are included in Appendix A). Subjects will be instructed to bring the used preparation components when they return for colonoscopy.

Subjects that have clinically significant electrolyte abnormalities, in the opinion of the principle investigator, based on Visit 1 laboratory results must be discontinued from the study. Subjects must be notified and instructed to return their unopened bowel preparation to the study center. These subjects will be classified as screen failures. Returned un-used study drug kits will not be re-dispensed to another subject.

#### **4.1.2. Dietary Restrictions**

Subjects may have a light breakfast on the day before colonoscopy, followed by clear liquids until the colonoscopy is completed the following day.

Examples of acceptable clear liquids are provided below:

- Water
- Strained fruit juices (without pulp) including apple, orange, white grape, or white cranberry
- Limeade or lemonade
- Gatorade/ Powerade
- Ginger ale
- Coffee or tea (do not use any dairy or non-dairy creamer)
- Chicken broth
- Gelatin desserts without added fruit or topping

Note: Purple/Red liquids (including red/purple varieties of Gatorade/Powerade), Milk and Alcoholic beverages are not permitted.

Non-compliance with the dietary restrictions will be documented, but will not require separate reporting as a protocol violation.

#### **4.1.3. Subject Questionnaires**

Subjects will be provided with a Preparation Questionnaire and Dietary Questionnaire to report document their preparation and dietary intake (refer to Appendix B for full questionnaires). Subjects will complete the Dietary Questionnaire starting the day before the colonoscopy. The Preparation Questionnaires will start the morning of colonoscopy with the first dose of study drug (Dose 1) and continue through the second dose (Dose 2). The time of all food/fluid ingestion will be recorded. Site staff must review the descriptions and times recorded on the questionnaire at Visit 2 to confirm that subjects were compliant with the dietary restrictions outlined in Section 4.1.2.

### **4.2. Bowel Preparation Administration**

On the day prior to their colonoscopy, subjects will begin following the protocol specified dietary restrictions (as outlined in Section 4.1.2) and completing their Dietary Questionnaires (refer to Appendix B). Approximately 8 hours prior to their scheduled

colonoscopy, subjects will begin consuming their bowel preparation according to the instructions provided by the study center (refer to Appendix A). Subjects will begin taking the second dose of bowel preparation 4 hours after starting the first dose.

#### **4.3. Visit 2**

After completing both preparation doses, subjects will return to the study center for their afternoon colonoscopy. Sites should attempt to schedule subjects a minimum of 4 days from date of screening to allow for receipt and review of screening lab results up to a maximum of 30 days. Visits scheduled beyond 30 days from Visit 1 will be considered a protocol violation and subjects must have a repeat blood draw.

Subjects will bring back their questionnaires and study personnel will review the questionnaires for completeness so that any missed responses can be captured. Subjects will complete a preference questionnaire. Any violations of the dietary restrictions must be confirmed with the subject.

Subject's vital signs will be repeated, a physical examination will be performed, and the subject will be queried for occurrence of adverse events and changes in concomitant medications. Blood samples will be collected for chemistry testing.

The colonoscopy will be performed by a physician according to the site's standard procedures and evaluated on a 4-point scale, as shown in Section 4.6. The colonoscopy procedure will be video recorded through the endoscope at selected research centers.

##### **4.3.1. Symptom Scale**

At Visit 2, subjects will complete a form asking them to report their overall experience with the preparation by checking the box that best describes the intensity of the following symptoms:

Symptom:	Scale:
Stomach Cramping	None – Severely Distressing

Stomach Bloating	None – Severely Distressing
Nausea	None – Severely Distressing

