## **5. ADVERSE EVENTS**

### **5.1. Adverse Event Definition and Reporting**

An Adverse Event (AE) is any untoward medical occurrence associated with the use of a drug in humans, whether or not considered drug related. An AE can therefore be any unfavorable and unintended sign (including a clinically significant abnormal laboratory finding), symptom, or disease temporally associated with the use of a medicinal (investigational) product. Subjects will be queried for any problems they experienced during and after preparation by site personnel. Symptoms on the symptom scale rated as 2 (mild) to 5 (severely distressing) must be reported as an adverse event. Colonoscopy and biopsy findings are not considered adverse events unless considered by the investigator to be related to the preparation or colonoscopy procedure.

Adverse event collection will commence at the time the patient provides informed consent. Subjects that have an ongoing treatment emergent adverse event or clinically significant abnormal laboratory value will be followed up approximately one week after colonoscopy.

Subjects will be instructed to promptly report adverse events to the Investigator. The Investigator will record date/time of report, date/time of onset, description of the adverse event, severity of adverse event, action(s) taken regarding treatment of the event, action(s) taken regarding study participation, duration of adverse event, and the Investigator's assessment of relationship of adverse event to study preparation.

The Investigator should assess the severity of each adverse event using the following categories:

Grade	Severity	Description
1	Mild	Barely noticeable, does not influence functioning causing no limitations of usual activities
2	Moderate	Makes participant uncomfortable, influences functioning causing some limitations of usual activities
3	Severe	Severe discomfort, treatment needed Severe and undesirable, causing inability to carry out usual Activities
4	Life threatening	Immediate risk of death, Life threatening or disabling (Must be reported as serious adverse event)
5	Fatal	Causes death of the participant (Must be reported as serious adverse event)

The Investigator should assess the relationship to study drug for each adverse event using the following categories:

Categories of Attribution:	Description
UNRELATED	There is no evidence of any causal relationship.

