## **5.2 Expected Adverse Events**

Because BLI4700 tablets contain the same active ingredient (sodium sulfate) as SUPREP, a similar adverse event profile is expected. In Phase 3 clinical trials, the most frequent adverse events reported by patients taking SUPREP (reported by >3% of patients) included overall discomfort, abdominal pain and distension, nausea, and vomiting.

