**9.2. Study Endpoints - Safety**

Adverse Events:

All subjects who took preparation in any amount will be included in the safety analysis. All adverse events will be summarized based on the principle of treatment emergence. A sign or symptom will be regarded as treatment-emergent if it was present prior to the first dose and subsequently worsened in severity, or was not present prior to the first dose but subsequently appeared.

In order to define treatment emergence for events with missing start or stop dates the following additional criteria will be used:

- if both the onset and resolution dates for a particular event are missing, then the event is considered treatment-emergent;
- if the onset date for an event is missing and the resolution date falls after the initiation of the first dose, then the event is considered treatment-emergent;

- if the onset date for an event falls after the initiation of the first dose and the resolution date is missing or present, then the event is considered treatment-emergent; and
- if the onset date for an event falls before the initiation of the first dose and the stop date is missing or present, then the event is not considered treatment-emergent.

Adverse events will be collected using MedDRA category designations for body system and preferred term. The number and percent of subjects who experienced each adverse event will be presented in a tabular form.

Vitals Signs and Physical Examination:

Vital signs and physical examination data will be summarized with descriptive statistics.

Laboratory Data:

Results of laboratory tests for the change from baseline (Screening) will be summarized with descriptive statistics.

Symptom Questionnaire Data:

Symptom questionnaire data for individual symptoms for Overall Experience (Stomach Cramping, Stomach Bloating and Nausea) will be presented.

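### Vomiting is an expected frequent event but is not on the Visit 2 symptom scale, so it risks less complete capture than the three prompted symptoms

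*Combined protocol and SAP*

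**What the plan says.** Section 4.3.1 has subjects complete a form at Visit 2 on which they "report their overall experience with the preparation by checking the box that best describes the intensity of the following symptoms". Three items follow: stomach cramping, stomach bloating and nausea, each running from none to severely distressing (for example, "Nausea None – Severely Distressing"). The analysis plan in Section 9.2 names the same three: "Symptom questionnaire data for individual symptoms for Overall Experience (Stomach Cramping, Stomach Bloating and Nausea) will be presented".

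Section 5.2 says the adverse-event profile should resemble that of SUPREP, whose most frequent events, each in more than 3% of Phase 3 patients, "included overall discomfort, abdominal pain and distension, nausea, and vomiting". Section 1, in the text below Table 2, gives a lower figure for the two pivotal SUPREP studies: "The expected symptoms of nausea and vomiting were the most frequent (1.3% each) within the gastrointestinal category".

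Section 5.1 ties the scale to the adverse-event data: "Symptoms on the symptom scale rated as 2 (mild) to 5 (severely distressing) must be reported as an adverse event". Vomiting has three other routes. Site staff ask every subject about problems during and after preparation (5.1), adverse events are queried at Visit 2 (4.3), and subjects are told to report events promptly (5.1). Section 9.2 puts all adverse events into one table by preferred term.

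**The concern.** Two kinds of event enter one table by different routes. Cramping, bloating and nausea are asked about by name, graded by the subject and, from mild upward, must be recorded. Vomiting is recorded only if the subject mentions it in answer to an open question or reports it unprompted. A gap between the nausea and vomiting rates could then partly reflect how the two were collected. Section 1 reports the same rate for both in the pivotal SUPREP studies, so such a gap would be easy to misread as a feature of the tablets.

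Subject-reported preparation symptoms are a named safety endpoint in the summary sheet, and the treatment is 24 swallowed tablets. Compliance is judged by counting tablets left over (Section 4.3.2). That count cannot show a dose that was swallowed and then vomited, so a vomiting record would also help in reading a failed preparation.

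**Working it through.** The plan states no figure for symptom capture, so there is nothing to reproduce. The check has two parts.

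**1. Sections side by side**

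| Symptom | Named as expected (5.2) | On the scale (4.3.1) and in the 9.2 symptom list | Mandatory adverse event from a scale rating (5.1) | Open query and self-report (4.3, 5.1) |
|---|---|---|---|---|
| Nausea | yes | yes | yes, rating 2 to 5 | yes |
| Cramping, bloating | yes, as abdominal pain and distension (my matching of terms) | yes | yes, rating 2 to 5 | yes |
| Vomiting | yes | no | no | yes |
| Overall discomfort | yes | no | no | yes |

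The prompted symptoms have every route that vomiting has, plus one that is structured and compulsory. That establishes unequal ascertainment. It does not show how many vomiting events would be missed.

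**2. Illustration of scale**

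Inputs:
- n = 60, the maximum in Section 9.3.
- True rate p = 1.3% (Section 1) or 3% (the floor of the more-than-3% statement in 5.2). I add 5% as an assumption, because 3% is only a floor.
- Capture c = 100%, 75% or 50%. These are assumptions; the documents give no capture rate.

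Expected recorded cases = n × p × c. Chance of recording none = (1 − p × c)^60.

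| True rate | Capture | Expected recorded cases | Chance of recording none |
|---|---|---|---|
| 1.3% | 100% | 60 × 0.013 = 0.78 | 0.987^60 = 0.456 |
| 1.3% | 75% | 60 × 0.00975 = 0.585 | 0.99025^60 = 0.556 |
| 1.3% | 50% | 60 × 0.0065 = 0.39 | 0.9935^60 = 0.676 |
| 3% | 100% | 60 × 0.03 = 1.80 | 0.97^60 = 0.161 |
| 3% | 75% | 60 × 0.0225 = 1.35 | 0.9775^60 = 0.255 |
| 3% | 50% | 60 × 0.015 = 0.90 | 0.985^60 = 0.404 |
| 5% | 100% | 60 × 0.05 = 3.00 | 0.95^60 = 0.046 |
| 5% | 75% | 60 × 0.0375 = 2.25 | 0.9625^60 = 0.101 |
| 5% | 50% | 60 × 0.025 = 1.50 | 0.975^60 = 0.219 |

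Halving capture adds about 24 percentage points at 3% (0.404 − 0.161) and 22 at 1.3% (0.676 − 0.456). The full-capture rows show what comes from the small sample alone: 16% at 3% and 46% at 1.3%.

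The two source rates also need reconciling. Section 1 puts nausea and vomiting at 1.3% each in the pivotal studies, while 5.2 puts them above 3% in Phase 3 trials. The protocol should say whether these come from different studies or different definitions.

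**The case against.** A reader might infer that vomiting is under-reported in this trial and will look rarer than it is. The documents do not support that. Every subject is asked about problems by site staff, adverse events are queried at Visit 2, and prompt reporting is required. Visit 2 falls on the day of dosing, with Dose 1 about 8 hours before colonoscopy and Dose 2 four hours after Dose 1 starts. Recall is over hours, for a discrete event. Capture could be close to complete.

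The Preparation Questionnaire, completed from Dose 1 through Dose 2, is a separate instrument from the Visit 2 scale. Its items are in Appendix B, of which only the heading is available here, so it may already ask about vomiting. What can be said is that 9.2 plans no vomiting result from any questionnaire.

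A reader might also infer that the omission spoils a comparison with SUPREP. The documents do not say how SUPREP events were elicited. If they were unsolicited, unprompted vomiting would be the like-for-like figure and prompted nausea the odd one. Section 5.2 plans no formal comparison in any case.

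Scale results are presented separately, so a reader can see which symptoms were prompted, but the adverse-event table still mixes the two kinds. Finally, this is an open-label pilot with no comparator or safety hypothesis, and which symptoms to solicit is partly a matter of preference. That limits the weight of the point but leaves the asymmetry standing.

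**Conclusion.** The point holds as a risk of less complete ascertainment of vomiting relative to cramping, bloating and nausea. It follows from Sections 4.3.1, 5.1, 5.2 and 9.2 read together and needs no outside source. The practical consequence is that the vomiting rate should not be set directly against the rates of the prompted symptoms.

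No estimate of bias is possible. The probabilities above rest on assumed capture and on two base rates that the protocol does not reconcile, and much of the chance of seeing no case comes from having at most 60 subjects. They show only that, with between 0.78 and 1.80 cases expected at the documents' two rates under full capture, losing one or two records could remove the signal. The matter does not threaten the study's validity, but the remedy is cheap and unequal capture is hard to repair after collection.

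**What to change.** - Add a vomiting item to the Visit 2 symptom form (4.3.1), as yes/no with number of episodes, which suits a discrete event better than an intensity scale. Add it to the symptom list in 9.2. If an Appendix B questionnaire already asks, name that item in 9.2 instead.
- State in 5.1 how the item becomes an adverse event, since the present rule is written for ratings of 2 to 5.
- In the adverse-event table, label prompted and unprompted events separately.
- Do not add an item for overall discomfort, although 5.2 lists it. It overlaps the existing three and, under the 5.1 rule, one complaint could be counted twice.
- Reconcile, or give separate sources for, the 1.3% in Section 1 and the more-than-3% in 5.2.

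The cost is one item on an existing form and a slightly higher event count. There is also a side effect to settle. Section 4.4 exempts symptoms prompted in the questionnaire from the 7-day return, so an ongoing vomiting event that would now lead to a return could fall under the exemption once it is prompted. Section 5.1, by contrast, describes one-week follow-up of ongoing treatment-emergent events without that exemption. The sponsor should reconcile these sections with the new item so that its effect on follow-up is intended.
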